9.2. Discontinuation from the Study

Subjects will be discontinued in the following circumstances:

- Enrollment in any other clinical study involving an investigational product or enrollment in any other type of medical research judged not to be scientifically or medically compatible with this study.
- Significant noncompliance with study drug administration.
- Investigator Decision
 - the investigator decides that the subject should be discontinued from the study.

- if the subject, for any reason, requires treatment with another therapeutic agent that has been demonstrated to be effective for treatment of the study indication, discontinuation from the study occurs prior to introduction of the new agent.
- Subject Decision
 - the subject requests to be withdrawn from the study.
- Sponsor Decision
 - the sponsor decides study participation should be stopped for medical, safety, regulatory, or other reasons consistent with applicable laws, regulations, and GCP.

Subjects who discontinue the study early will have end-of-study procedures (Day 5 for SAD; Day 56 for MAD) performed as shown in the Schedule of Events ([Appendix 2](#)).

9.3. Subjects Lost to Follow-up

A subject will be considered lost to follow-up if he or she repeatedly fails to return for scheduled visits and is unable to be contacted by the study site. Site personnel are expected to make diligent attempts to contact subjects who fail to return for a scheduled visit or were otherwise unable to be followed up by the site.

10. Study Assessments and Procedures

[Appendix 2](#) lists the Schedule of events, detailing the study procedures and their timing.

[Appendix 3](#) lists the laboratory tests that will be performed for this study.

[Appendix 6](#) provides a summary of the maximum number and volume of invasive samples, for all sampling, during the study.

Unless otherwise stated in subsections below, all samples collected for specified laboratory tests will be destroyed within 60 days of receipt of confirmed test results. Certain samples may be retained for a longer period, if necessary, to comply with applicable laws, regulations, or laboratory certification standards.

Investigators must document their review of each laboratory safety report.

10.1. Efficacy Assessments

Efficacy will not be assessed in this study. Pharmacodynamics will be assessed as described in [Section 10.6](#).

10.2. Adverse Events

Investigators are responsible for monitoring the safety of subjects who have entered this study and for alerting Chorus or its designee to any event that seems unusual, even if this event may be considered an unanticipated benefit to the subject.

The investigator is responsible for the appropriate medical care of subjects during the study.

The investigator remains responsible for following, through an appropriate health care option, AEs that are serious or otherwise medically important, considered related to the investigational product or the study, or that caused the subject to discontinue the investigational product before completing the study. The subject should be followed until the event resolves, stabilizes with appropriate diagnostic evaluation, or is reasonably explained. The frequency of follow-up evaluations of the AE is left to the discretion of the investigator.

After the informed consent form (ICF) is signed, study site personnel will record, via CRF, the occurrence and nature of each subject's preexisting conditions, including clinically significant signs and symptoms of the disease under treatment in the study. Additionally, site personnel will record any change in the condition(s) and the occurrence and nature of any AEs.

The investigator will interpret and document whether an AE has a reasonable possibility of being related to study treatment or a study procedure, taking into account the disease, concomitant treatment, or pathologies.

A "reasonable possibility" means that there is a cause and effect relationship between the investigational product, study device, and/or study procedure and the AE.

Planned surgeries should not be reported as AEs unless the underlying medical condition has worsened during the course of the study.

If a subject's investigational product administration is discontinued as a result of an AE, study site personnel must report this to Chorus or its designee via CRF or designated data transmission methods.

10.2.1. Serious Adverse Events

An SAE is any AE from this study that results in one of the following:

- death
- initial or prolonged inpatient hospitalization
- a life-threatening experience (that is, immediate risk of dying)
- persistent or significant disability/incapacity
- congenital anomaly/birth defect
- events considered significant by the investigator based upon appropriate medical judgment

Study site personnel must alert Chorus, or its designee, of any SAE within 24 hours of investigator awareness of the event via a sponsor-approved method. If alerts are issued via telephone, they are to be immediately followed with official notification on study-specific SAE forms. This 24-hour notification requirement refers to the initial SAE information and all follow-up SAE information.

Although all AEs are recorded in the CRF after signing informed consent, SAE reporting begins after the subject has signed informed consent and has received investigational product.

However, if an SAE occurs after signing informed consent, but prior to receiving investigational product, AND is considered "reasonably possibly related" to a study procedure then it MUST be reported.

Investigators are not obligated to actively seek AEs or SAEs in subjects once they have discontinued from and/or completed the study (the subject summary CRF has been completed). However, if the investigator learns of any SAE, including a death, at any time after a subject has been discharged from the study, and he/she considers the event reasonably possibly related to the study treatment or study participation, the investigator must promptly notify Chorus.

Pregnancy (maternal or paternal exposure to investigational product) does not meet the definition of an AE. However, to fulfill regulatory requirements any pregnancy should be reported following the SAE process to collect data on the outcome for both mother and fetus.

10.2.1.1. Suspected Unexpected Serious Adverse Reactions

Suspected unexpected serious adverse reactions (SUSARs) are serious events that are not listed in the IB and that the investigator identifies as related to investigational product or procedure. United States 21 CFR 312.32, European Union Clinical Trial Directive 2001/20/EC, and the associated detailed guidances or national regulatory requirements in participating countries require the reporting of SUSARs. The sponsor/designee has procedures that will be followed for

the recording and expedited reporting of SUSARs that are consistent with global regulations and the associated detailed guidances.

10.2.2. Complaint Handling

Chorus/designee collects product complaints on investigational products and drug delivery systems used in clinical trials in order to ensure the safety of study participants, monitor quality, and to facilitate process and product improvements.

Subjects should be instructed to contact the investigator as soon as possible if he or she has a complaint or problem with the investigational product (or drug delivery system) so that the situation can be assessed.

10.3. Treatment of Overdose

Refer to the IB (Section 7.3.9) and/or Product Label (LY and/or comparator) for details regarding an overdose of investigational product.

10.4. Safety

10.4.1. Laboratory Tests

For each subject, laboratory tests detailed in [Appendix 3](#) should be conducted according to the Schedule of Events ([Appendix 2](#)). When collections for clinical laboratory tests are scheduled at the same time point as ECG collections, ECGs must be recorded prior to any blood sampling.

10.4.2. Vital Signs

For each subject, vital signs measurements should be conducted according to the Schedule of Events ([Appendix 2](#)) and following the study specific recommendations included in an Appendix or the Manual of Operations for the study.

Respiratory rate (collected at Screening and, for Part B only, Day -1, Hour -1), BP, pulse, and temperature should be measured after at least 5 minutes supine.

Orthostatic BP and pulse rate will be obtained from each subjects at all specified vital sign collection time points in Part A and on Day -1 through study discharge at specified vital sign collection time points in Part B. Supine BP and pulse rate will be measured after the subject has been supine for at least 5 minutes; standing BP and pulse rate will be measured in triplicate at 1, 2, and 3 minutes after the subject has been standing.

Unscheduled orthostatic vital signs should be assessed, if possible, during any AE of dizziness or posture-induced symptoms. Additional vital signs may be measured during each study period if warranted and agreed upon between the sponsor and investigator.

10.4.3. Electrocardiograms

For each subject, ECGs should be collected according to the Schedule of Events ([Appendix 2](#)) and the study specific recommendations included in a Manual of Operations for the study that will be maintained that the CRU.

When ECG collections are scheduled at the same time point as any other tests the order of collection will be as follows:

- 1) ECGs.
- 2) vital signs.
- 3) any clinical laboratory, PK, PD, or biomarker blood sampling.

Any clinically significant findings from ECGs that result in a diagnosis and that occur after the subject receives the first dose of the investigational product, should be reported to Chorus, or its designee, as an AE via CRF or designated data transmission methods.

In Part A, a 12-lead digital ECG will be collected from each subject as a single tracing during Screening and in triplicate (spaced approximately 1 minute apart) at all other specified ECG collection time points. In Part B, ECGs will be collected as a single tracing during Screening and Day -2. Twelve-lead ECGs will be collected in triplicate on Day -1 through study discharge at specified ECG collection time points.

Subjects must be supine for at least 5 minutes prior to ECG collection and remain supine but awake during ECG collection. Electrocardiograms may be obtained at additional times, when deemed clinically necessary. All ECGs recorded should be stored at the investigational site.

Electrocardiograms will be interpreted by a qualified physician (the investigator or qualified designee) at the site as soon after the time of ECG collection as possible, and ideally while the subject is still present, to determine whether the subject meets entry criteria at the relevant visit(s) and for immediate subject management, should any clinically relevant findings be identified.

If a clinically significant finding is identified (including, but not limited to, changes in QT/QTc interval from baseline) after enrollment, the investigator will determine if the subject can continue in the study. The investigator, or qualified designee, is responsible for determining if any change in subject management is needed, and must document his/her review of the ECG printed at the time of collection. Any new clinically relevant finding should be reported as an AE.

10.4.4. Safety Monitoring

The Chorus CRP/scientist, or designee, will monitor safety data throughout the course of the study.

Chorus will review SAEs within time frames mandated by company procedures to meet local regulatory requirements. The Chorus CRP will consult with the functionally independent Global Patient Safety therapeutic area physician or clinical research scientist when appropriate, and periodically review:

- trends in safety data
- AEs of special interest here.

If a study subject experiences elevated ALT or AST $\geq 3 \times$ ULN or ALP/GGT/elevated total bilirubin $\geq 2 \times$ ULN, clinical and laboratory monitoring should be initiated by the investigator. Details for hepatic monitoring depend upon the severity and persistence of observed laboratory test abnormalities (see [Appendix 5](#)). To ensure subject safety and compliance with regulatory guidance, the investigator is to consult with the Chorus designated CRP regarding collection of specific recommended clinical information and follow-up laboratory tests ([Appendix 4](#)).

If anemia (defined as a hemoglobin or hematocrit below normal reference range in the laboratory) develops during dosing, additional evaluation with a peripheral blood film, reticulocyte count, haptoglobin, indirect bilirubin, and LDH will be implemented.

In the event that safety monitoring uncovers an issue that needs to be addressed by unblinding at the group level, additional analyses of the safety data will be conducted by the personnel included in the Unblinding/Blinding Plan.

10.5. Pharmacokinetics

At the visits and times specified in the Schedule of Events ([Appendix 2](#)), serial venous blood samples of approximately 4 mL each will be collected to determine the plasma concentrations of LY3202328, simvastatin (Part B only), and atorvastatin (Part B only). Blood samples for PK characterization will be collected after single- and multiple-dose administration and follow-up visits in Parts A and B. Trough concentrations over multiple days during Part B will also be assessed.

Sample timing may be adjusted based on information gained during the study, while the total number of samples described in the Schedule of Events ([Appendix 2](#)) will be planned. Up to 2 additional PK samples may be collected per period if needed and with appropriate documentation of rationale for the additional samples.

Instructions for the collection and handling of blood samples will be provided by the sponsor. The actual date and time (24-hour clock time) of each sampling will be recorded.

Drug concentration information that may unblind the study will not be reported to investigative sites or blinded personnel until the study has been unblinded.

Urine samples will be collected and pooled over the 24 hour dosing period to determine the urine concentrations and for the characterization of renal clearance of LY3202328 in Part A. Total urine output for the appropriate period post investigational product administration will be collected, pooled, and refrigerated. A predose urine sample will be collected to serve as a blank. The final urine sample will be collected at a time that coincides with a PK sample. At the end of the collection period (24 hours), the total urine volume will be recorded. Urine samples will be used to determine creatinine, quantification of LY3202328, and urine creatinine measurements. Approximately 20 mL of urine from the 24-hour urine collection will be stored for potential LY3202328 metabolite identification and other exploratory testing (10 mL each). Although not currently planned, urine sample collection may be added to Part B depending on results obtained from Part A.

Remaining plasma and urine PK samples may also be stored for LY3202328 metabolite identification.

At the visits and times specified in the Schedule of Events ([Appendix 2](#)) venous blood samples of approximately 4 mL each will be collected to determine serum creatinine measurements.

10.5.1. Bioanalysis

Samples will be analyzed at a laboratory approved by the sponsor and stored at a facility designated by the sponsor.

Concentrations of LY3202328, simvastatin, and atorvastatin will be assayed using validated analytical methods. Samples collected from placebo-treated subjects in each period are not planned for analyses. Simvastatin and atorvastatin analyses will only occur on samples collected during the 24 hour post dosing periods starting on Day -7 and Day 29.

Bioanalytical samples collected to measure investigational product concentrations will be retained for a maximum of 1 year following last subject visit for the study. During this time, samples remaining after the bioanalyses may be used for exploratory analyses (such as metabolism and/or protein binding work).

10.6. Pharmacodynamics

Pharmacodynamic blood samples of approximately 10 mL will be collected in Parts A and B as specified in the Schedule of Events ([Appendix 2](#)).

Plasma TG, TC, and high-density lipoprotein cholesterol (HDL-c) (to calculate LDL-c and non-HDL-c) will be assessed in the fasted state for the first 4 hours postdose and then again during the post-prandial period following a high-fat meal administration at 4 hours postdose in Part B. Changes in these PD markers from baseline (Day -1) and Day 28 will be assessed at each dose level to find at least 1 dose level that shows evidence of target engagement by a decrease in fasting or post-prandial lipids.

The lipid lowering ability of LY3202328 in subjects with a statin-free background will be quantified by TG, TC, and HDL-c (to calculate LDL-c and non-HDL-c) in Parts A and B, and by LDL-c ultracentrifugation methods in Part B only.

10.6.1. Exploratory Biomarker Analyses

Biomarker research is performed to address questions of relevance to drug disposition, target engagement, pharmacodynamics, mechanism of action, variability of subject response (including safety), and clinical outcome. Sample collection is incorporated into clinical studies to enable examination of these questions through measurement of biomolecules including DNA, RNA, proteins, lipids, and other cellular elements.

Plasma samples for exploratory biomarker research will be collected at the times specified in the Schedule of Events ([Appendix 2](#)). Fasting LDL-c, FFA, β -hydroxybutyrate, ApoB100, ApoC3, PCSK9, and Lp(a) measured at baseline (Day -1), Day 28, and Follow-up will be evaluated in Part B.

Samples will be retained for a maximum of 1 year after the last subject visit, or until testing is complete after the last subject visit for the study at a facility selected by Chorus or its designee.

10.7. Pharmacogenomic/Stored Samples

A blood sample will be collected for pharmacogenetic analysis in Part A and Part B as specified in the Schedule of Events ([Appendix 2](#)) where local regulations allow.

DNA will be isolated from the pharmacogenetic sample to test genetic polymorphisms that may affect:

- the absorption, disposition, metabolism, or excretion of LY3202328;
- response to LY3202328;
- adverse reactions to LY3202328;
- unusual response to LY3202328 (either safety or PD response; genome-wide association studies may be used); and/or
- dyslipidemia-related gene polymorphisms.

Additionally, the samples obtained from the biomarker collections in Parts A and/or B will be stored and may be used as follows:

- plasma and serum for biomarker analysis to help explore and understand the mechanism of action of LY3202328 and/or dyslipidemia; and
- residue plasma samples from lipid collections may be stored for exploratory testing of other lipid pathways.

Samples will not be used to conduct unspecified disease or population genetic research either now or in the future. Samples will be used to investigate variable response to LY3202328 and to investigate genetic variants thought to play a role in dyslipidemia. Assessment of variable response may include evaluation of AEs or differences in efficacy.

All samples will be coded with the subject number. These samples and any data generated can be linked back to the subject only by the investigative site personnel.

Samples will be retained for a maximum of 15 years (DNA) or 5 years (plasma and serum) after the last subject visit, or for a shorter period if local regulations and/or ERBs impose shorter time limits, for the study at a facility selected by Chorus or its designee. This retention period enables use of new technologies, response to regulatory questions, and investigation of variable response that may not be observed until later in the development of LY3202328 or after LY3202328 is commercially available.

11. Statistical Considerations and Data Analysis

11.1. Sample Size Determination

Part A (SAD): 9 statin-free, overweight, healthy subjects for Cohort 1 and 2 (each subject to receive investigational product at 2 active dose levels and placebo) and a possible additional cohort (each subject to receive investigational product at 1 active dose level [600 mg] or placebo). This sample size is customary for Phase 1 studies evaluating safety, tolerability, and PK parameters, and is not powered on the basis of statistical hypothesis testing.

Part B (MAD): 10 statin-free, overweight, dyslipidemic subjects per cohort (8 subjects to receive active investigational product: 2 subjects to receive placebo) is a customary sample size for a Phase 1b MAD study evaluating safety, tolerability, and PK parameters, and is not powered on the basis of statistical hypothesis testing.

Additional subjects may be enrolled at any time if agreed to by the Sponsor to replace drop-outs or discontinued subjects with the goal to complete up to 18 subjects in Part A and 40 subjects in Part B. Replacements are not required. Replacement subjects for Part A may not be required to complete all periods.

11.2. Populations for Analyses

The study population will consist of up to 18 statin-free, overweight, healthy male and female subjects in Part A and up to 40 statin-free, overweight, healthy male and female subjects with dyslipidemia in Part B, aged 18 to 70 years old, inclusive, for males, or 40 to 70 years old, inclusive, for females. Two analysis populations will be used in this study:

- The Safety population will include all subjects who receive at least 1 dose of LY3202328.
- The PK population will include all subjects who receive LY3202328 (and simvastatin or atorvastatin in Part B) and have sufficient concentration data to obtain reliable estimates of the key PK parameters (C_{max} and AUC).

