6.1.2. Part B: Multiple Ascending Dose – Drug-Drug Interaction Design

Part B will comprise a double-blinded, MAD, staggered parallel design in dyslipidemic (TG: 150 to 499 mg/dL; LDL-c: 100 to 200 mg/dL), statin-free, overweight (BMI 27.0 to 40.0 kg/m²), male and female subjects investigating the safety, tolerability, and PK of multiple doses of LY3202328 and the effect of LY3202328 on simvastatin and atorvastatin exposure.

A total of 40 subjects will be enrolled and divided evenly into 4 study periods (n=10 subjects per study period) to evaluate 4 dose levels of LY3202328 (Periods 5, 6, 7, and 8 at 5, 20, 100, and 300 mg, respectively, are planned).

Within each cohort, 5 subjects will be stratified to the simvastatin DDI assessment and 5 subjects will be stratified to the atorvastatin DDI assessment. Within each stratum subjects will be randomly assigned 4:1 to receive LY3202328 or placebo so that 8 subjects will receive LY3202328 and 2 subjects receive placebo in each cohort. Subjects will receive QD dose of LY3202328 or placebo in the morning in the fasted state for 29 total days. For DDI assessment, subjects will also receive a single atorvastatin or simvastatin dose a week prior to LY3202328 treatment initiation, and on Day 29 after initiation of LY3202328 daily dosing (coadministered with LY3202328).

The dose levels intended for study in Part B may change based upon data from Part A, but will range from as low as 1 mg and are not to exceed the highest dose evaluated in Part A. Any dose level used in Part B will not start until the safety data from the same or higher dose level in Part A has been reviewed by the safety committee responsible for dose escalation decisions.

Potential subjects will be screened to assess their eligibility to enter the study within 42 days prior to study entry (i.e., prior to Check in for Part B). For each cohort, subjects will be admitted to the CRU on Day –8 (the day before administration of a single dose of simvastatin or atorvastatin) and will be discharged 24 hours postdose (Day –6).

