11.3. Statistical Analyses

Statistical analysis of this study will be the responsibility of Chorus or its designee.

Pharmacokinetic/PD and safety analyses will be conducted on the PK and Safety populations, respectively.

Additional exploratory analyses of the data will be conducted as deemed appropriate. Study results may be pooled with the results of other studies for population PK analysis purposes to avoid issues with post-hoc analyses and incomplete disclosures of analyses.

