11.3.1.2. Statistical Evaluation of Safety

The primary endpoint of this study is the number and severity of treatment-emergent adverse events (TEAEs), clinical laboratory abnormalities, changes in vital sign measurements, and other safety endpoints after administration of LY3202328 or placebo. Summary statistics will be provided by dose group and for all study subjects combined wherever appropriate. For

continuous variables, summary statistics will include number of subjects, mean, median, SD, minimum, and maximum. Categorical endpoints will be summarized using number of subjects, frequency, and percentages. Additional analysis will be performed if warranted upon review of the data.

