2.2.1 Analysis Populations

Two analysis populations will be used in this study:

- Safety data and baseline information will be analyzed using the **Safety Population**. The Safety Population is defined as all randomized subjects who received at least one dose of study treatment.
- Pharmacodynamics (PD) data will be analyzed using the **PD Population**. The PD Population is defined as all subjects who received at least one dose of LY and have both a baseline and post-baseline assessment of at least one PD parameter.

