4.3 Baseline Lipids

For enrollment in Part B subjects are required to have screening triglyceride (TG) levels between 150 and 499 mg/dL, inclusive, and screening low-density lipoprotein cholesterol (LDL-c) levels between 100 and 200 mg/dL, inclusive. These lipids levels are allowed for enrollment in Part A but they are not required. During the Part B screening visit, fasting measurements of TG, total cholesterol (TC), and high-density lipoprotein cholesterol (HDL-c) will be obtained from plasma samples. LDL-c and non-HDL-c will then be derived as follows:

$$\text{LDL-c} = \text{TC} - (\text{TG}/5 + \text{HDL-c}), \text{ and}$$

$$\text{non-HDL-c} = \text{TC} - \text{LDL-c}.$$

Descriptive statistics for these five lipid parameters for subjects enrolled in Part B will be provided for each of the treatment groups and overall.

5 Concomitant Medications

Concomitant medications will be defined as medications, other than simvastatin and atorvastatin, taken on or after the date of first dose of randomly assigned study treatment (LY or placebo). This includes all medications initially taken prior to the date of first dose of randomly assigned study medication but with a stop date that is either missing or after the date of first dose of randomly assigned study medication. Those medications where the stop date is documented as prior to the date of first dose of randomly assigned study medication will be classified as prior medications. The prior medications will not be included in any summary reports.

The number (percent) of subjects who receive each concomitant medication, based on the WHODD preferred drug name, will be tabulated for Part B, but it is not planned to summarize in table format the concomitant medication usage for Part A of the study. However, by-subject listings of all concomitant medications that includes WHODD preferred drug name will be prepared separately for Parts A and B.

6 Pharmacodynamics Analyses

Pharmacodynamics (PD) analyses for this study will be based on fasting and post-prandial lipid profiles, fasting free fatty acids (FFA), β -hydroxybutyrate, apolipoprotein (Apo) B100, ApoC3,

proprotein convertase subtilisin/kexin type 9 (PCSK9), lipoprotein (a) [Lp(a)] and insulin, and body weight. All of these assessments will be collected longitudinally during the study.

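### Protocol 11.2 limits the Safety population to LY3202328 recipients; applied literally it would drop all 8 planned Part B placebo subjects, and it conflicts with the primary endpoint and the SAP

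*Protocol*

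**What the plan says.** Protocol 11.2 states: "The Safety population will include all subjects who receive at least 1 dose of LY3202328". Protocol 11.3 ties the analyses to the populations: "Pharmacokinetic/PD and safety analyses will be conducted on the PK and Safety populations, respectively".

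Protocol 11.3.1.2 sets the primary endpoint as adverse events, laboratory abnormalities, vital-sign changes "and other safety endpoints after administration of LY3202328 or placebo". Protocol 6.4 explains that placebo is there as the negative control against which adverse events are characterized.

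For Part B, Protocol 6.1.2 describes a staggered parallel design. On numbers it says: "A total of 40 subjects will be enrolled and divided evenly into 4 study periods (n=10 subjects per study period"). Within each statin stratum, subjects are "randomly assigned 4:1 to receive LY3202328 or placebo so that 8 subjects will receive LY3202328 and 2 subjects receive placebo in each cohort".

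The SAP differs. SAP 2.2.1 states: "The Safety Population is defined as all randomized subjects who received at least one dose of study treatment". SAP 2.2.2 lists Placebo as one of the five Part B treatment groups, and SAP 7 runs all safety analyses on the SAP's Safety population. SAP 2.2.1 does not define *study treatment*. The nearest gloss is in SAP 5, where concomitant medications are those "taken on or after the date of first dose of randomly assigned study treatment (LY or placebo").

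**The concern.** The two documents give different membership rules for the population behind the primary endpoint, and neither acknowledges the difference or says which one prevails. The protocol also disagrees with itself: an endpoint measured after LY3202328 or placebo cannot be reported in Part B from a population that requires a dose of LY3202328.

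At stake is the concurrent control. If the protocol sentence were followed, the Part B summaries of adverse events, laboratory values and vital signs would have no placebo column. That is the comparison that Protocol 6.4 gives as the reason for including placebo.

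**Working it through.** **Inputs.** Part B has 4 cohorts of 10, with 8 LY3202328 and 2 placebo in each (Protocol 6.1.2). Each cohort has two strata of 5, randomized 4:1 (same section). Part A has 18 subjects in 2 cohorts of 9, each scheduled for 2 LY3202328 doses and 1 placebo dose (Protocol 6.2). Three subjects per Part A cohort receive placebo first (Figure GSEA.1).

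**Reproducing the plan's figure.**
- Part B total: 4 × (8 + 2) = 40, as stated.
- By stratum: 5 subjects at 4:1 gives 4 LY3202328 and 1 placebo. Then 1 placebo × 2 strata × 4 cohorts = 8 placebo, and 40 − 8 = 32 LY3202328.

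**Planned Safety population under each rule, with everyone completing.**
- Part B, Protocol 11.2 as written: 32, with 0 placebo.
- Part B, SAP 2.2.1: 40, with 8 placebo.
- Difference: 8/40 = 20% of Part B, and 8/8 of its placebo group.
- Both parts: 18 + 32 = 50 against 18 + 40 = 58. The difference is 8/58 = 13.8%.

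**Part A.** A subject who completes as scheduled receives LY3202328 and is included under either rule, so the planned loss is 0. The ceiling is 3 × 2 = 6, reached only if every subject who starts on placebo leaves before a first LY3202328 dose. The documents give no dropout rate, so the range is 0 to 6 and no expected number can be given.

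**Membership by type of subject.**

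| Subject | Protocol 11.2 as written | SAP 2.2.1 | Proposed wording |
|---|---|---|---|
| Part B, LY3202328 (32 planned) | in | in | in |
| Part B, placebo (8 planned) | out | in | in |
| Part A, completes as scheduled (18 planned) | in | in | in |
| Part A, starts on placebo, leaves before any LY3202328 (0 to 6) | out | in | in |
| Part B, Day -7 statin only (number not given) | out | unclear | out |

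The last row arises because Part B subjects are randomized and given a statin on Day -7, before LY3202328 or placebo starts on Day 1. SAP 3.2 expects such cases, since it counts subjects who were randomized but not treated with LY3202328 or placebo. Protocol 8.1 lists the statins among the treatments administered. The SAP 5 gloss points to LY3202328 or placebo only, but SAP 2.2.1 does not carry that restriction.

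**The case against.** The strongest reply is that the SAP already settles the matter. Its Safety Population, its Part B Placebo group and its section 7 together keep all 8 placebo subjects and give the tables a placebo column. A reader of Protocol 11.2 alone might infer that the placebo subjects will be lost from the primary analysis. The documents do not support that: the loss occurs only if the protocol definition is the one applied. This part of the reply stands and limits the consequence.

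A second reply is that LY3202328 in Protocol 11.2 is shorthand for blinded study drug. The protocol does use it loosely. Section 6.1.2 gives Part B subjects a container of LY3202328 doses, while footnote t of the Part B schedule describes the contents as LY3202328 or placebo; section 8.5 is similarly loose. A drafting slip is plausible, and nothing shows a deliberate choice to drop the controls. The shorthand reading does not remove the conflict, however. The PK population in the same section uses the drug name literally, since Protocol 10.5.1 does not plan to assay placebo subjects' samples. The next subsection, 11.2.1, uses the broader term *study treatment*.

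Third, safety reporting is descriptive: SAP 7.2 rules out statistical testing of treatment-emergent events, and Protocol 11.1 says the sample size is not powered. Protocol 8.3.1 bases escalation on subjects completing Day 5 or Day 14 procedures, without reference to this population. All of that is correct. It means that no hypothesis test or escalation rule depends on the sentence, but the primary endpoint still needs one membership rule.

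**Conclusion.** The inconsistency is real and should be corrected, with a conditional consequence. Protocol 11.2, read as written, excludes 8 of 40 planned Part B subjects (20%), which is the entire placebo group. It also excludes between 0 and 6 planned Part A subjects, depending on withdrawal before any LY3202328 dose. Under SAP 2.2.1 none of these subjects is excluded.

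The counts assume that enrolment and allocation go as planned. They leave out replacement subjects and any separate 600 mg cohort, for which the documents give no placebo number. It would be wrong to report that the placebo group is lost, or that six Part A subjects will be: the first depends on which document is followed, and the second is a ceiling.

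Copying the SAP sentence into the protocol would not be a full cure, because its undefined term leaves the status of a statin-only subject open.

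**What to change.** Amend the Safety population in Protocol 11.2 to: *all randomized subjects who receive at least one dose of LY3202328 or placebo*. Use the same words in SAP 2.2.1 in place of *study treatment*.

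The cost is one sentence in each document. Data collection does not change. Programs that already count subjects dosed with LY3202328 or placebo need no change; a program that admits a subject on the Day -7 statin alone would need its population flag revised.

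While SAP 2.2.1 is open, its PD Population should also be checked. It too requires a dose of LY3202328, although SAP 6.1.2 contrasts the dose levels with placebo. That is a separate matter and is not counted here.
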